### 2.6.5.2 Vital signs

Vital signs assessments are performed in order to characterize basic body function. The following parameters will be collected: height (cm), weight (kg), body temperature (°C), heart rate (beats per minute), systolic and diastolic blood pressure (mmHg).

The summaries will include all on-treatment assessments available no later than 56 days after the last study treatment administration date (see Section 2.1.1) as well as including all short-term and long-term assessments cumulatively in separate summaries.

The number and percentage of participants with on-treatment notable vital sign values (high/low) will be presented.

Vital signs parameters will be listed, and periods of assessment (screening, on-treatment, short term and long term follow-up) will be flagged.

For analysis of vital signs, the clinically notable vital sign criteria are provided in Table 2-1 below.

**Table 2-1 - Clinically notable changes in vital signs**

Vital sign (unit)	Clinically notable criteria	
	above normal value	below normal value
Weight (kg)	increase $\geq 20\%$ from baseline	decrease $\geq 10\%$ from baseline
Systolic blood pressure (mmHg)	$\geq 180$ with increase from baseline of $\geq 20$	$\leq 90$ with decrease from baseline of $\geq 20$
Diastolic blood pressure (mmHg)	$\geq 105$ with increase from baseline of $\geq 15$	$\leq 50$ with decrease from baseline of $\geq 15$
Pulse rate (bpm)	$\geq 100$ with increase from baseline of $> 25\%$	$\leq 50$ with decrease from baseline of $> 25\%$

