#### **8.4.4 Height and Weight**

Height will be taken at screening, week 1 of cycle 4 treatment, EoT, last visit of short-term FUP, and every six months during long-term FUP.

Weight will be taken at screening, before each Lutathera administration, at the EoT, and every six months during long-term FUP. In addition, weight should be measured for each CrCl calculation (i.e. on the days when chemistry tests are taken).

Height will be obtained in centimeters (cm) and body weight in kilograms (kg) and rounded to the nearest 0.1 kg. Weight will be obtained in indoor clothing, without shoes.

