**Nephrotoxicity:** Since Lutathera is cleared through the kidneys and reabsorbed by the kidneys, the kidneys have always been considered the “critical organs”. An infusion of amino acid is used for kidneys protection by inhibition of tubular reabsorption of Lutathera. Pursuant to these risk minimization efforts and in addition to the criteria of dose-modifying toxicities and criteria of inclusion (at baseline and before subsequent treatments) pertinent to renal function measurements, renal and urinary tract toxicities are considered AESI. Investigators must report as AESI renal toxicities including renal failure (ranging from significantly reduced measured or estimated creatinine clearance to clinically overt renal failure other than that of obvious non-IMP-induced origin), suspected radiation nephropathy of any type, such as radiation-induced thrombotic microangiopathy (manifested with, e.g., proteinuria, hypertension, edema, anaemia, decrease serum haptoglobin), or general symptoms and signs of acute radiation toxicity (e.g., increased frequency and urgency of urination, nocturia, dysuria, bladder spasm, bladder obstruction, genitourinary ulceration or necrosis).

**Endocrine (hypothalamic-pituitary and growth) disorders:** Since the potential effect of the Lutathera treatment on the pituitary-gonadal and pituitary-thyroid axes is not well described in the adolescent population, the endocrine effects will be closely monitored via specific biomarkers. Any suspected endocrine toxicity should be considered AESI regardless of severity.

**Effects on bone development:** Radiation exposure has a potential effect on the overall quantity and quality of bone by interfering with the trabecular architecture through increased osteoclast activity and decreased osteoblast activity. Biomarkers of bone metabolism help to detect the metabolic imbalance and identify bone toxicities. Any suspected bone toxicity should be considered AESI regardless of severity.

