### 1.1 Study design

This is a multicenter, open-label, single-arm study to evaluate the safety and dosimetry of Lutathera in adolescent patients aged 12 to <18 years old with somatostatin receptor positive GEP-NETs or PPGLs. The study will enroll at least 8 adolescent patients across GEP-NETs and PPGLs, including a minimum of 3 adolescents with GEP-NET.

The study schedule for each participant consists of the screening period (up to 2 weeks) followed by the treatment period (4 treatment administrations at 8-week (+/- 1 week) intervals), and the follow-up period (5 years).

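### SAP 2.6.5.2 plans no age- and sex-standardised growth summary, although height is measured on a schedule, and its notable vital-sign criteria are the same at every age from 12 to under 18

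*SAP*

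**What the plan says.** The study enrols "adolescent patients aged 12 to <18 years old" (SAP 1.1). SAP 2.6.5.2 lists height, weight, temperature, heart rate and blood pressure as the parameters collected, and refers to Table 2-1 ("Clinically notable changes in vital signs") for the notable criteria. That table flags weight on "increase $\geq 20\%$ from baseline" or "decrease $\geq 10\%$ from baseline". It flags high systolic pressure at 180 mmHg or more with a rise of at least 20, and high diastolic pressure at 105 mmHg or more with a rise of at least 15. It also has low blood-pressure and pulse limits. No criterion varies with age, sex or height, and height has no row.

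On the period covered, SAP 2.6.5.2 says two things. The number and percentage of patients with notable values are given for the on-treatment period. The summaries cover on-treatment assessments "as well as including all short-term and long-term assessments cumulatively in separate summaries". Baseline is the last value on or before first dose (SAP 2.1.1) and is never re-set.

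Protocol 8.4.4 takes height at screening, Cycle 4 Week 1, end of treatment, the last short-term visit, "and every six months during long-term FUP". Protocol 4.5 names growth among the additional paediatric safety concerns, and Protocol 10.1.5 has an AESI category headed "Endocrine (hypothalamic-pituitary and growth) disorders". The Amendment 02 log records that height visits were added so that height is monitored twice a year.

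**The concern.** Growth is a safety question that the sponsor raised, and height is the only direct measure of it taken on a fixed schedule in every patient. The SAP collects height but does not say how it will be turned into evidence about growth. Mean height or weight by visit rises in any group of growing adolescents, and it depends on the mix of ages and sexes at that visit. Such a summary cannot separate normal growth from slowed growth.

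The weight criteria do not fill the gap. The low flag needs a 10% loss, so a patient who should be gaining weight and gains none is never flagged. The blood-pressure criteria are also the same from 12 to 17 years. Protocol 4.5 and 6.2.3 name hypertension as a concern in PPGL, and 7 of the 11 patients enrolled by 14 December 2023 had PPGL.

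What is at stake is the secondary objective on long-term safety. The height data will exist, but the plan specifies no summary that would answer the growth question.

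**Working it through.** The plan states no figure on this point to reproduce. The check sets Table 2-1 against the parameter list, the schedule and the period rules, then converts the weight flag into a growth rate.

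**1. Scheduled heights per completer** (Protocol 8.4.4 and Table 8-2). Screening, Cycle 4 Week 1, end of treatment and Week 25 give 4. Six-monthly visits from month 12 to month 60 after the last dose give 9. Total: 4 + 9 = 13.

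**2. Length of each window** (SAP 1.1 and 2.1.1). Four doses at 8-week intervals put the last dose 24 weeks (168 days) after the first.
- On-treatment: 168 + 56 = 224 days = 32 weeks = 0.613 years.
- To the end of short-term follow-up: 168 + 183 = 351 days = 0.961 years.
- To the end of the study: 168/365.25 + 5 = 5.46 years.

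**3. Yearly gain needed to reach +20% from the fixed baseline.** Rate = 1.20^(1/T) − 1.

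| Window | T (years) | Compound gain needed per year |
|---|---|---|
| On-treatment | 0.613 | 34.6% |
| To end of short-term follow-up | 0.961 | 20.9% |
| To end of 5-year follow-up | 5.46 | 3.4% |

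If all three dose intervals stretched to 16 weeks, the on-treatment window would be 3 × 112 + 56 = 392 days = 1.073 years, and the rate needed would be 18.5%.

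**4. The same in kilograms.** The documents give no weights or growth rates, so these baselines are assumptions. For 35 to 65 kg, a 20% gain is 7 to 13 kg. Over 0.613 years that is 11.4 to 21.2 kg a year; over 5.46 years it is 1.3 to 2.4 kg a year. From an assumed 45 kg (a 9 kg gain), 2 kg a year reaches the flag in 9/2 = 4.5 years and 5 kg a year in 9/5 = 1.8 years.

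**5. What the fixed cut-offs leave out.**
- Weight change of 0%: above −10% and below +20%, so never flagged in any window.
- Systolic 110 to 175 mmHg: the rise of 65 meets the change condition, but 175 is below 180, so it is not flagged.
- Diastolic 60 to 104 mmHg: the rise of 44 meets the change condition, but 104 is below 105, so it is not flagged.

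**6. Is the period clear?** For laboratory data, SAP 2.6.4 states that the listed summaries are repeated with the follow-up periods included. SAP 2.6.5.2 promises cumulative follow-up summaries of vital signs, but the only summary it describes is the on-treatment notable count. Whether Table 2-1 is applied in follow-up, and what those follow-up summaries contain for height and weight, is left unstated.

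**The case against.** The strongest reply is that growth is watched in several ways. All vital-sign parameters, height included, are listed with their period, and with about 11 patients each course can be read by eye. IGF-1, BALP and NTX or CTX are measured, and their shift or grade summaries are repeated for follow-up. Suspected endocrine, growth or bone toxicity is an AESI at any severity. This stands against any inference that growth impairment cannot be seen. It does not supply a planned assessment. The biomarkers are not growth itself. In follow-up, AESIs other than secondary malignancies are reported only if judged related to treatment, and are listed rather than summarised.

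A reader might also infer that the Table 2-1 flags run for more than five years and so mostly count normal growth. The SAP does not say this. The notable count is on-treatment, and in that window the weight flag needs a gain far above any rate assumed in the working. The 3.4% figure applies only if the flag is carried into follow-up.

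On blood pressure, Table 2-1 is not the only route. Significant changes go on the AE page, clinically significant changes close to dosing are AESIs, and extra measurements are allowed in PPGL (Protocol 8.4.3 and 10.1.5). A rise to 175 mmHg misses the table but need not go unrecorded. Patients also turn 18 during follow-up, so paediatric percentiles would not fit the whole study. Both points limit the remedy without removing the gap. Finally, the documents give no source for the cut-offs, so calling them adult values would be a judgement.

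**Conclusion.** The point holds as a gap in the planned analysis. The criteria are not age-referenced, Table 2-1 has no height criterion, and the visible text specifies no age- and sex-standardised growth summary, despite about 13 heights per completer and a stated growth concern. Growth is not systematically assessed, which is weaker than saying that it is invisible.

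The weight-gain flag is a secondary matter. It would do little harm in the period where the SAP counts it (about 35% a year needed) and would mislead only if extended to the end of follow-up (about 3.4% a year needed). The SAP should settle which applies. The high blood-pressure limits leave large rises out of the notable-value table, but not necessarily out of the AE record.

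This rests on the nominal 8-week schedule, on assumed baseline weights and yearly gains where kilograms are quoted, and on the visible text. Part of the SAP after section 2.7 is redacted, and nothing is inferred from that. The study is descriptive, so no hypothesis test depends on this. The change is a low-cost improvement to the long-term safety analysis and should be made.

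**What to change.** Amend SAP 2.6.5.2 and Table 2-1; this concerns analysis only.

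- Convert height, weight and BMI to age- and sex-standardised z-scores against a named growth reference. Summarise value and change from baseline by visit through long-term follow-up, with BMI where height is taken.
- Add a notable criterion on change in height z-score, with its threshold stated before the analysis.
- Add age-referenced blood-pressure flags for assessments made while the patient is under 18, and keep the existing cut-offs beside them.
- State that the 20% weight-gain flag applies on-treatment only, with weight or BMI z-score change used in follow-up. Keep the 10% weight-loss flag.

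No new data are needed: age, sex, height, weight and blood pressure are already collected. The cost is programming against external growth and blood-pressure references, and a departure from the project-standard vital-sign tables.

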## 2.7 Pharmacokinetics and dosimetry analysis supporting secondary objectives

As part of the secondary objectives, PK and dosimetry data will be analysed in the context of the modeling and extrapolation performed using adult data (as detailed in the modeling report). The adult PK (radiolabel plasma concentrations) data was fitted to a two compartment model with a zero-order input and first-order elimination. The adult kidney and bone marrow dosimetry data were described by [REDACTED]

Plots of observed PK and dosimetry data from adolescent participants overlaid with predictions using the adult model will be first generated to evaluate if the pediatric population is adequately characterized by the model from the adult population. Adolescent PK parameters (e.g., CL, Cmax) will also be compared to those parameters derived from the adult population, to ensure that adolescent values lie within those estimates determined from the adult population. Other methods may also be applied if deemed valuable in the assessment of the adolescent data. These analyses will be based on the DAS and PKAS.

Then, pooled analyses using all adolescent and adult participants for dosimetry data will be performed. For that, parameters from the models will be re-estimated based on population-based non-linear mixed effects modeling using appropriate software. Covariates from the adult model (i.e., dose and creatinine clearance for dosimetry modeling) as well as other covariates such as age, weight and body surface area will be re-evaluated and inter-relationships re-assessed. Model qualification will use graphical methods, such as visual inspection of different diagnostic plots, precision of any parameter estimates (estimated  $\pm$  standard error), Visual Predictive Check (VPC) plots (stratified by adult and adolescent populations) as well as decreases in both between-subject variability and residual variability.

Further details on the PK and dosimetry modeling will be given in a separate modeling plan.

Finally, the following model-based PK parameters will be reported for each adolescent participant:

- AUCinf: area under the concentration time curve from 1st administration to infinity
- AUClast: Area under the concentration time curve from 1st administration to the last observed concentration
- Cmax: maximum blood concentration
- tmax: sampling time at which Cmax is reached
- CL: systemic clearance
- V1: Volume of distribution of the central compartment
- V2: Volume of distribution of the peripheral compartment
- Q2: Inter-compartmental clearance.

Other parameter estimates may be determined as deemed appropriate.

Final

Final

[REDACTED]

[REDACTED]

[REDACTED]

[REDACTED]

### 3 Sample size calculation

No formal sample size or power calculations were made in the context of this safety study.

For the interim analysis, the sample size is proposed to be a minimum of five patients across the GEP-NET and PPGL indications, including a minimum of 2 GEP-NET patients. Simulations from adult kidney and bone marrow dosimetry models suggested that a clinical trial that has enrolled between 5 and 10 subjects should have the ability to define the median dosimetry values without significant risk of exceeding pre-defined thresholds. Thus, 5 patients across indication should be acceptable.

Dosimetry at the organs of interest is the key measure in this study and is not expected to differ between PPGL and GEP-NET patients (confirmed by the preliminary data). Therefore, the data on PPGL patients will be included in the interim analysis both separately from GEP-NET and combined with GEP-NET to support the overall comparison between pediatric and adult patients. Safety data, to which PPGL patients will also contribute, will be supplemented with literature that provides further justification for the acceptability of this proposal.

For the primary analysis, the overall sample size of 8 participants is deemed sufficient to confirm similar organ dosimetry results in the adolescent population compared to the ones in adults.

Modeling and simulation analysis shows that a mean (standard deviation) of the absorbed dose in the kidney of approximately 18 Gy (SD 8) is expected in the adolescent population. Assuming a standard deviation of 8, a sample size of 8 patients will produce a two-sided 95% confidence interval with a distance from the mean to the limits that is equal to 6.68.

Additionally, a sample size of 8 patients produces an adequate probability of observing acute toxicities (See Table 3-1). Indeed, in the phase III NETTER-1 study grade 3/4 adverse drug reactions related to Lutathera treatment were observed in 30% of patients. The probability to detect similar events assuming a true incidence rate of 30% in this study population is 94.2% with 8 patients.

Final

**Table 3-1 - Likelihood of observing at least one patient with acute toxicity for a sample size of 8 patients and incidence of acute toxicities**

Sample size	Acute toxicities true incidence rate				
	10%	20%	30%	40%	50%
	8	57.0	83.2	94.2	98.3
					99.6

## 4 Change to protocol specified analyses

No change from protocol specified analysis was made.

## 5 Appendix

### 5.1 Imputation rules

#### 5.1.1 AE, ConMeds and safety assessment date imputation

**Table 5-1 - Imputation of start dates (AE, CM) and assessments (LB, EG, VS)**

Missing Element	Rule
day, month, and year	
 
No imputation will be done for completely missing dates
 

day, month	
 
If available year = year of study treatment start date then 
 
If stop date contains a full date and stop date is earlier than study treatment start date then set start date = 01JanYYYY
 
Else set start date = study treatment start date.
 
 
 
If available year > year of study treatment start date then 01JanYYYY
 
If available year < year of study treatment start date then 01JulYYYY
 

day	
 
If available month and year = month and year of study treatment start date then 
 
If stop date contains a full date and stop date is earlier than study treatment start date then set start date= 01MONYYYY.
 
Else set start date = study treatment start date.
 
 
 
If available month and year > month and year of study treatment start date then 01MONYYYY
 
If available month and year < month year of study treatment start date then 15MONYYYY
 

**Table 5-2 - Imputation of end dates (AE, CM)**

Missing Element	Rule (*=last treatment date plus 56 days not > (death date, cut-off date, withdrawal of consent date)) 
day, month, and year	
 
• Completely missing end dates (incl. ongoing events) will be imputed by the end date of the on-treatment period*
 

day, month	
 
• If partial end date contains year only, set end date = earliest of 31DecYYYY or end date of the on-treatment period *
 

day	
 
• If partial end date contains month and year, set end date = earliest of last day of the month or end date of the on-treatment period*
 

1. if start date is > 56 last treatment date plus 56 days then use the same rules but the end date of the on-treatment period is defined as (death date, cut-off date, withdrawal of consent date)	

Any AEs and ConMeds with partial/missing dates will be displayed as such in the data listings.

Any AEs and ConMeds which are continuing as per data cut-off will be shown as 'ongoing' rather than the end date provided.

The above imputations are only used for analyses of duration of AEs and concomitant medications.

### 5.1.1.1 Other imputations

#### Incomplete date of initial diagnosis of cancer and date of most recent recurrence

Missing day is defaulted to the 15th of the month and missing month and day is defaulted to 01-Jan.

#### Incomplete assessment dates for tumor assessment

All investigation dates (e.g. MRI scan, CT scan) must be completed with day, month and year. If one or more assessment dates are incomplete but other investigation dates are available, this/these incomplete date(s) are not considered for calculation of the assessment date and assessment date is calculated as the latest of all investigation dates (e.g. MRI scan, CT scan) if the overall response at that assessment is CR/PR/SD/UNK. Otherwise – if overall response is progression – the assessment date is calculated as the earliest date of all investigation dates at that evaluation number. If all measurement dates have no day recorded, the 1st of the month is used. If the month is not completed, for any of the investigations, the respective assessment will be considered to be at the date which is exactly between previous and following assessment. If a previous and following assessment is not available, this assessment will not be used for any calculation.

## **Applying the cut-off to tumor assessment**

For tumor related assessments, if an evaluation has some assessments done prior to cut-off date and others after the cut-off date, then the evaluation is considered post-cut-off date and will be excluded from analysis.

### **5.2 AEs coding/grading**

Adverse events are coded using the Medical dictionary for regulatory activities (MedDRA) terminology.

AEs will be assessed according to the Common Terminology Criteria for Adverse Events (CTCAE) version 5.0.

The CTCAE represents a comprehensive grading system for reporting the acute and late effects of cancer treatments. CTCAE grading is by definition a 5-point scale generally corresponding to mild, moderate, severe, life threatening, and death. This grading system inherently places a value on the importance of an event, although there is not necessarily proportionality among grades (a grade 2 is not necessarily twice as bad as a grade 1).

### **5.3 Laboratory parameters derivations**

Grade categorization of lab values will be assigned programmatically as per NCI Common Terminology Criteria for Adverse Events (CTCAE) version 5.0. The calculation of CTCAE grades will be based on the observed laboratory values only, clinical assessments will not be taken into account. The latest available version of the document based on the underlying CTCAE version 5.0 at the time of analysis will be used. For laboratory tests where grades are not defined by CTCAE v5.0, results will be graded by the low/normal/high (or other project-specific ranges, if more suitable) classifications based on laboratory normal ranges.

A severity grade of 0 will be assigned for all non-missing lab values not graded as 1 or higher. Grade 5 will not be used. For laboratory tests that are graded for both low and high values, summaries will be done separately and labelled by direction, e.g., sodium will be summarized as hyponatremia and hypernatremia.

